4.2 Study Schedule of Activities

Study Procedures	Follow-up Period (Visit Window)				
	1	2	3	5 (-1 to +1)	8/ET (-1 to +1)
Study Days					
Informed Consent	X				
COVID19 Screening & SARS-CoV-2 Rapid Antigen Test***	X				
Medical History & Physical Examination	X	Changes since last visit only	Changes since last visit only	Changes since last visit only	X
Oropharyngeal Assessment	X*	Changes since last visit only	Changes since last visit only	Changes since last visit only	X
Urine Pregnancy Test	X				X
Concomitant Medication History/New	Baseline	Changes since last visit only			
Comprehensive Metabolic Panel & CBC	X				X
Vital Signs	X				X
Methemoglobin	X				X
Adverse Event Assessment / Reactogenicity	Baseline	X	X	X	X
Demographics, Inclusion / Exclusion Review	X				
Diary Dispensation/Collection	X				X
Treatment at Site	X**	X**	X**		
Biospecimen collection for viral assays (3 specimens)****	X		X	X	X
COVID-19 Severity Score	X				X
Collect RD-X19 Device	NA			Cohort 1	Cohort 2

*On Day 1 to be evaluated 30 minutes after first illumination at site.

**Only one treatment will be done on site, other treatment will be done at home, i.e. if afternoon appointment, subject will complete morning treatment at home and afternoon treatment administered at the site. For scheduling purposes, recommended interval between treatment is approximately 8 – 12 hours but not \leq 4 hours.

***Subjects presenting at the time of screening that have tested positive via a SARS-CoV-2 rapid antigen test at or within the past 24 hours of the screening visit and can provide documentation confirming proper identification, the date of the test and testing location, positivity of the result, and name/identity of the assay used to generate the result, are also eligible for enrollment and the rapid antigen test does not have to be repeated at the site.

**** At Baseline and days 3, 5, and 8, subjects will provide two saliva specimens and an oropharyngeal swab for virology endpoint assessments. One saliva specimen will be collected, preserved, and shipped fresh to a central lab for assessment of SARS-CoV-2 mRNA via RT-qPCR. The second specimen and the oropharyngeal swab will be collected in separate collection tubes, frozen, and stored at the site and shipped to a central lab at the end of each cohort.

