All AEs were of short duration, with resolution typically reached the same day or within 24 hours. Since study subjects used the RD-X19 device approximately every 12 hours for 14 contiguous days, there was a continuous temporal association with RD-X19 device use and incident AEs during the course of RD19-01-3Q20. By definition, all local site reactions were attributed to the device; all were mild and transient and there was no pattern of increasing frequency with repeated, cumulative dosing.

Population-based epidemiological data for headaches and nausea were considered when establishing device attribution. Approximately 40% of the general adult population have weekly headache and over 30% suffer from intermittent bouts of nausea of unknown origin. Given the frequencies of headache and nausea reported in RD19-01-3Q20 are less than those reported in population-based epidemiological studies, the relationship with the RD-X19 device cannot be determined.

In summary, the RD19-01-3Q20 Phase I trial demonstrated that EmitBio™ RD-X19 is a safe device, consistent with the sponsor's and IRB's original conclusion that RD-X19 is a NSR device.

Risks to Privacy

Subjects will be asked to provide personal health information (PHI). All attempts will be made to keep this PHI confidential within the limits of the law. However, there is a chance that unauthorized persons will see the subject's PHI. All study records will be kept in a locked file cabinet or maintained in a locked room at the participating clinical trial site(s). Electronic files will be password protected. Only people who are involved in the conduct, oversight, monitoring, or auditing of this trial will be allowed access to the PHI that is collected. Any publications from this trial will not use information that will identify subjects by name.

Organizations that may inspect and/or copy research records maintained at the participating clinical trial site(s) for quality assurance (QA) and data analysis include groups such as the IRB and the FDA.

A description of this clinical trial will be posted on <http://www.ClinicalTrials.gov>. This web site does not include information that can identify subjects.

There may be other risks, discomforts or side effects that are entirely unknown at this time.

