This clarification outlines the sponsors decision to allow enrollment for up to a 20% overage of the proposed number of subjects.

1. Up to 36 total subjects meeting enrollment criteria related to COVID-19 signs and symptoms may be enrolled per each dose Cohort. This clarification is intended to allow for enrollment of Hispanic subjects for at least 7 days post translation of all study documents into Spanish that was approved and available on November 25th, 2020 for Cohort 1.

STATISTICAL ANALYSIS PLAN

Protocol EB-P12-01

Version 2.0
January 25, 2021

A Phase I/II Randomized, Dose Escalation Study to Evaluate the Safety and Antiviral Activity of the RD-X19 Device in SARS-CoV-2 Infected Individuals with Uncomplicated COVID-19

EmitBio Inc.

[name]
[name]

Approved By:

/s/ [name]	01/25/2021
[name] Director of Statistics Symbio LLC	Date
/s/ [name]	01/25/2021
[name], MPH, PhD Chief Medical Officer EmitBio Inc.	Date
/s/ [name]	01/25/2021
[name] Chief Scientific Officer EmitBio Inc.	Date

CONFIDENTIAL

Table of Contents

1	Purpose of Statistical Analysis Plan	3
2	Study Objectives	3
3	Study Design and Sample Size Determination	3
3.1	Study Design.....	3
3.2	Sample Size Determination.....	4
4	Populations To Be Analyzed	4
5	Planned Analyses	5
5.1	Methodological Considerations	5
5.2	Handling of Missing Data	5
5.2.1	Missing Efficacy Endpoints.....	5
5.2.2	Missing or Incomplete Dates for Adverse Events and Concomitant Medications	5
5.3	Demographics and Baseline Characteristics	6
5.4	Subject Accountability.....	6
5.5	Efficacy Variables and Analyses	6
5.5.1	Analysis of Primary Efficacy Endpoint.....	7
5.5.2	Analysis of Secondary Efficacy Endpoints	7
5.5.3	Analysis of Exploratory Efficacy Endpoint.....	8
5.6	Safety and Tolerability Variables and Analyses	8
5.6.1	Adverse Events.....	8
5.6.2	Vital Signs	9
5.6.3	Methemoglobin	9
5.6.4	Other Assessments	9
6	Tables and Listings	10
7	Appendices.....	10
7.1	Study Schedule of Activities.....	10
7.2	List of Summary Tables, Data Listings and Figures.....	12

Statistical Analysis Plan

1 Purpose of Statistical Analysis Plan

The purpose of the statistical analysis plan is to describe in detail all the data, statistical methods, and summary tables required to implement the statistical analysis of Clinical Study Protocol EB-P12-01 (Section 10 in the study protocol version 2.0 (Amendment 1), dated November 06, 2020).

2 Study Objectives

[figure not shown]

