3.1 Study Design

For the purpose of exploring the above objectives, the study will be conducted as a randomized, double-blind, sham-controlled dose escalation study in SARS-CoV-2 infected individuals with outpatient COVID-19 at two dosing schedules.

This study plans to enroll into two treatment arms within two escalating dose cohorts:

Volunteers meeting all inclusion criteria and none of the exclusion criteria will be randomized to the RD-X19 treatment arm or the sham treatment arm within each cohort in a 2:1 ratio (20 RD-X19 : 10 sham), according to a fixed schedule via a permuted block design and stratified by clinical site. Light will be administered twice daily locally to the mouth and throat only for four days for Cohort 1 and for seven days for Cohort 2.

The clinic visits will occur at:

- Visit 1 / Screening, Enrollment & Randomization

- Visit 2 / Day 2
- Visit 3 / Day 3
- Visit 4 / Day 5 (\pm 1 day)
- Visit 5 / Day 8 (\pm 1 day) / Early Termination (ET)

Assessments of treatment response will occur on study days 3 and 5, with a final determination of efficacy made on day 8 (inclusive).

Efficacy will be evaluated through evaluation of viral load through quantitation of SARS-CoV-2 mRNA by RT-qPCR and via quantitation of replication competent virus by viral titer. Severity of the symptoms of disease will also be aggregated to produce a composite COVID-19 severity score. Safety and tolerability assessments will include solicited and unsolicited adverse events (AEs), physical examinations, vital signs, and clinical laboratory tests.

One unblinded interim analysis is planned upon completion of all subjects in Cohort 1. The results of the interim analysis will be reviewed by a safety monitoring team and a recommendation will be made to the sponsor on whether enrollment should proceed for the next cohort at the next planned dose or at a reduced dosing frequency (e.g. once daily). The study is designed to evaluate at least 2 dosing schedules, ascending, or descending based on safety of each previous cohort.

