3.2 Sample Size Determination

The study is hypothesis generating in nature. Hence, the sample size was selected for convenience.

The target number of subjects randomized is 60 in total, and 30 per cohort (20 subjects to RD-X19 and 10 subjects to sham).

4 Populations To Be Analyzed

Three subject populations are defined as follows:

- (1) Safety: This population will include all subjects who receive at least 1 study treatment. The Safety Population will be used for analysis of safety and tolerability data. Subjects will be analyzed based on actual treatment received.
- (2) Intent-to-Treat (ITT): This population will include all randomized subjects who receive treatment and were not discontinued due to a significant abnormality from the baseline CMP and CBC tests. This population will be used for all efficacy analyses as the primary population. Subjects will be analyzed based on randomized treatment, regardless of the actual treatment received.
- (3) Per-Protocol Population (PP): This population will include subjects who complete the study and did not have a major protocol deviation (MPD). The PP population will be used for supportive analysis of the efficacy endpoints. MPDs are those that could have interfered with the administration of treatment or the precise evaluation of treatment efficacy.

MPDs may include but will not be limited to the following:

- Violation of inclusion/exclusion criteria;
- Use of prohibited concomitant medications during the treatment period;
- No Day 3 Visit;

- Returned for Day 8 Visit outside the designated visit window;
- Was not compliant with the dosing regimen.

All MPDs will be identified before the database lock and study unblinding for analysis.

5 Planned Analyses

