Note 2: Time to sustained alleviation is calculated as the number of hours from the first dose to the time of the occurrence of sustained symptoms alleviation. Subjects who did not

achieve sustained alleviation at the last assessment of the study are considered censored at the time of the last assessment.

Note 3: Percentiles and 95% CI of median are derived using the Kaplan-Meier method. P-values for treatment comparison are from Log Rank Test.

Source: Listing 16.2.6.1.2, 16.2.5.3

O:\Studies\EmitBio\EB-P12-01\Biometrics\Programs\Tables\xxx.sas ran on Month Day, Year at hh:mm on data from Month Day, Year.

Figure 15.3.1 - Kaplan-Meier Plot of Time to Sustained Alleviation of COVID-19 Symptoms for Intent-to-Treat Population

Figure 15.3.2 - Kaplan-Meier Plot of Time to Sustained Alleviation of COVID-19 Symptoms for Per-Protocol Population

Table 14.3.1.1 - Treatment-Emergent Adverse Events by System Organ Class and Preferred Term for Safety Population

System Organ Class Preferred Term	4 Days RD-X19 (N=XX) n (%)	7 Days RD-X19 (N=XX) n (%)	Sham (N=XX) n (%)
Subjects Reporting at Least One Adverse Event	XX (XX.X)	XX (XX.X)	XX (XX.X)
System Organ Class #1	XX (XX.X)	XX (XX.X)	XX (XX.X)
Preferred Term #1	XX (XX.X)	XX (XX.X)	XX (XX.X)
Preferred Term #2	XX (XX.X)	XX (XX.X)	XX (XX.X)
...			
System Organ Class #2	XX (XX.X)	XX (XX.X)	XX (XX.X)
Preferred Term #1	XX (XX.X)	XX (XX.X)	XX (XX.X)
Preferred Term #2	XX (XX.X)	XX (XX.X)	XX (XX.X)
...			

Counts reflect numbers of subjects reporting one or more TEAE that map to the MedDRA system organ class/preferred term. At each level of summarization (system organ class or preferred term), subjects reporting more than one TEAE are counted only once.

Source: Listing 16.2.7

O:\Studies\EmitBio\EB-P12-01\Biometrics\Programs\Tables\xxx.sas ran on Month Day, Year at hh:mm on data from Month Day, Year.

Table 14.3.1.2 - Treatment-Emergent Adverse Events by System Organ Class, Preferred Term and Severity for Safety Population

System Organ Class Preferred Term	Severity	4 Days RD-X19 (N=XX) n (%)	7 Days RD-X19 (N=XX) n (%)	Sham (N=XX) n (%)
Subjects Reporting at Least One Adverse Event	Mild	XX (XX.X)	XX (XX.X)	XX (XX.X)
	Moderate	XX (XX.X)	XX (XX.X)	XX (XX.X)
	Severe	XX (XX.X)	XX (XX.X)	XX (XX.X)
System Organ Class #1	Mild	XX (XX.X)	XX (XX.X)	XX (XX.X)
	Moderate	XX (XX.X)	XX (XX.X)	XX (XX.X)
	Severe	XX (XX.X)	XX (XX.X)	XX (XX.X)
Preferred Term #1	Mild	XX (XX.X)	XX (XX.X)	XX (XX.X)
	Moderate	XX (XX.X)	XX (XX.X)	XX (XX.X)

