Counts reflect numbers of subjects reporting one or more TEAE that map to the MedDRA system organ class/preferred term. At each level of summarization (system organ class or preferred term), subjects reporting more than one TEAE are counted only once under the earliest Study Day when the event of greatest severity was reported.

Source: Listing 16.2.7

O:\Studies\EmitBio\EB-P12-01\Biometrics\Programs\Tables\xxx.sas ran on Month Day, Year at hh:mm on data from Month Day, Year.

Table 14.3.2 – Reactogenicity by Visit for Safety Population

Study Visit	Category	4 Days RD-X19 n (%)	7 Days RD-X19 n (%)	Sham n (%)
Visit 1 /Day 1	N	XX	XX	XX
	n (%) subject with illumination site pain	XX (XX.X)	XX (XX.X)	XX (XX.X)
	n (%) subject with illumination site erythema	XX (XX.X)	XX (XX.X)	XX (XX.X)
	n (%) subject with illumination site Edema/Induration	XX (XX.X)	XX (XX.X)	XX (XX.X)
	n (%) subject with other pain, redness, swelling, or lesion of the oral mucosa	XX (XX.X)	XX (XX.X)	XX (XX.X)
Visit 2 /Day 2	N	XX	XX	XX
	n (%) subject with illumination site pain	XX (XX.X)	XX (XX.X)	XX (XX.X)
	n (%) subject with illumination site erythema	XX (XX.X)	XX (XX.X)	XX (XX.X)
	n (%) subject with illumination site Edema/Induration	XX (XX.X)	XX (XX.X)	XX (XX.X)
	n (%) subject with other pain, redness, swelling, or lesion of the oral mucosa	XX (XX.X)	XX (XX.X)	XX (XX.X)
Visit 3 /Day 3	...			
Visit 4 /Day 5	...			
Visit 5 /Day 8/ET	...			

Source: Listing 16.2.9.1

O:\Studies\EmitBio\EB-P12-01\Biometrics\Programs\Tables\xxx.sas ran on Month Day, Year at hh:mm on data from Month Day, Year.

Table 14.3.3 – Oropharyngeal Assessment by Visit for Safety Population

Study Visit	Category	4 Days RD-X19 n (%)	7 Days RD-X19 n (%)	Sham n (%)
Overall*	N	XX	XX	XX
	Normal	XX (XX.X)	XX (XX.X)	XX (XX.X)
	Abnormal	XX (XX.X)	XX (XX.X)	XX (XX.X)
Visit 1 /Day 1	N	XX	XX	XX
	Normal	XX (XX.X)	XX (XX.X)	XX (XX.X)
	Abnormal	XX (XX.X)	XX (XX.X)	XX (XX.X)
Visit 2 /Day 2	N	XX	XX	XX
	Normal	XX (XX.X)	XX (XX.X)	XX (XX.X)
	Abnormal	XX (XX.X)	XX (XX.X)	XX (XX.X)
Visit 3 /Day 3	...			
Visit 4 /Day 5	...			
Visit 5 /Day 8/ET	...			

*For Overall, Normal category includes subjects with a normal result for all visits; Abnormal category includes subjects with an abnormal result at any visit.

Source: Listing 16.2.9.2

O:\Studies\EmitBio\EB-P12-01\Biometrics\Programs\Tables\xxx.sas ran on Month Day, Year at hh:mm on data from Month Day, Year.

Table 14.3.4 – Vital Signs by Visit for Safety Population

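### The final safety tables pool 4-day and 7-day sham users in one Sham column, so for events tied to device use the 7-day arm looks worse, and the 4-day arm better, than sham under no effect

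*Combined protocol and SAP*

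**What the plan says.** SAP 3.1 randomises subjects "within each cohort in a 2:1 ratio (20 RD-X19 : 10 sham"), with light given twice daily "for four days for Cohort 1 and for seven days for Cohort 2". The schedule row "Collect RD-X19 Device" in Protocol 4.2 (version 2.0) places collection at the Day 5 visit for Cohort 1 and the Day 8 visit for Cohort 2. Sham subjects therefore have two different lengths of device use.

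SAP 5.6 groups all safety output by treatment assignment, and the coding in SAP 5.5.1 makes sham one level of a three-level treatment variable. The shells in SAP 7.2 follow suit. "Table 14.3.1.1 - Treatment-Emergent Adverse Events by System Organ Class and Preferred Term for Safety Population", Tables 14.3.1.2 to 14.3.1.4, "Table 14.3.2 – Reactogenicity by Visit for Safety Population" and Table 14.3.3 all have columns for 4 Days RD-X19, 7 Days RD-X19 and one Sham. SAP 5.6.1 also asks for site reactions and unsolicited AEs to be tabulated for each of Days 1 to 8. No final summary table separates sham by cohort; cohort appears only in the by-subject listings. The interim tables use Cohort 1 alone.

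On timing of reactions, Protocol 5.2.1 reports from Phase I: "All AEs were of short duration, with resolution typically reached the same day or within 24 hours".

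**The concern.** If reactions are short-lived, they cluster in the days when the device is used. A sham subject with 4 days of use has less opportunity to report one than a sham subject with 7. Averaging the two gives a sham rate that is too high a yardstick for the 4-day arm and too low for the 7-day arm. A reader comparing columns would take a difference in exposure time for a device effect, with opposite signs for the two schedules.

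True device reactions are not strictly needed for this. Protocol 9.2.10 lets an event be classed as related on close timing alone, and as unrelated when timing does not fit. Clarification Memorandum #1 has new COVID-type symptoms from Day 4 onward recorded as AEs, with attribution left to the investigator. On Days 5–7 Cohort 2 sham subjects are still treating and Cohort 1 sham subjects are not, so the same background symptom could be classed differently by cohort. That would reach the Related rows of Table 14.3.1.3.

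The SAP's interim section treats the cohorts as unconnected when it justifies unblinding the sponsor to Cohort 1. Merging their sham subjects in the final tables sits awkwardly with that.

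**Working it through.** **1. Sham numbers.** SAP 3.2: "The target number of subjects randomized is 60 in total, and 30 per cohort". At 2:1, 30 × 2/3 = 20 active and 30 × 1/3 = 10 sham, so 2 × 30 = 60, as stated. Clarification Memorandum #2: "Up to 36 total subjects meeting enrollment criteria related to COVID-19 signs and symptoms may be enrolled per each dose Cohort". That is 30 × 1.2 = 36, or 12 sham at 2:1. The Cohort 1 share of pooled sham, w, is 10/20 = 50% as planned, and runs from 10/22 = 45.5% to 12/22 = 54.5% if only one cohort uses the overage.

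**2. Exposure.** Mean sham use is (4 + 7)/2 = 5.5 days. That is 5.5/4 = 1.38 times the 4-day arm and 5.5/7 = 0.79 times the 7-day arm.

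**3. Cumulative tables (14.3.1.1–14.3.1.3).** Assume the same constant daily risk h in active and sham while the device is used, and none afterwards. Incidence is 1 − (1 − h)^4 or 1 − (1 − h)^7; pooled sham is their mean at w = 0.5. The documents give no sham rate, so h is an assumption.

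| h | 4 days | Pooled sham | 7 days | 4-day − sham | 7-day − sham |
|---|---|---|---|---|---|
| 3% | 11.5% | 15.3% | 19.2% | −3.9 | +3.9 |
| 5% | 18.5% | 24.4% | 30.2% | −5.8 | +5.8 |
| 10% | 34.4% | 43.3% | 52.2% | −8.9 | +8.9 |

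For orientation, Phase I had 12 of 25 subjects with any AE over 14 days on the active device. As a constant daily risk that is h = 1 − (13/25)^(1/14) = 4.56%, giving 17.0%, 22.5% and 27.9%, or ±5.4 points (about one subject in 20). At h = 1% the distortion is ±1.4 points. With 12 + 10 sham subjects the table's differences become −3.5/−5.3/−8.1 and +4.2/+6.3/+9.7 points.

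**4. Daily tabulations, Days 5–7.** Let p be the daily rate on the device and q the rate after stopping, equal in active and sham. Pooled sham is wq + (1 − w)p. Then 7-day minus sham is w(p − q), and 4-day minus sham is −(1 − w)(p − q). At w = 0.5 and q = 0, p = 5%, 10% or 30% gives ±2.5, ±5 or ±15 points. If q = p/2 these halve; if q = p or p = 0 they vanish. On Days 1–3 every subject is on the schedule, so the distortion is zero.

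**5. Precision.** Root mean squared error of active minus sham is √(bias² + active variance + sham variance), with 20 active subjects and the rates in step 3:

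| h | 4-day: pooled sham (20) | 4-day: own sham (10) | 7-day: pooled sham (20) | 7-day: own sham (10) |
|---|---|---|---|---|
| 3% | 11.4 | 12.3 | 12.5 | 15.3 |
| 5% | 14.1 | 15.1 | 15.1 | 17.8 |
| 10% | 17.6 | 18.4 | 18.0 | 19.3 |

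With zero events, the one-sided 95% upper bound is 1 − 0.05^(1/10) = 25.9% for 10 subjects and 1 − 0.05^(1/20) = 13.9% for 20.

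**The case against.** Five points can be made for leaving the tables alone.

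- **The tables do not drive the decision.** The primary safety measure concerns device-related SAEs and patterns of grade 2 or higher device-related events, not a rate difference from sham. Escalation rests on the interim, where sham is unmixed. The two RD-X19 schedules can be compared without the Sham column. The safety shells carry no differences, intervals or p-values. All this stands and limits the importance; it does not make a side-by-side reading of the columns fair.
- **The size is assumed.** No sham reaction rate is given. If the sham device provokes few reactions, or events are unrelated to use, the distortion tends to zero, since both cohorts are followed to Day 8. This stands.
- **Splitting costs precision.** In all six scenarios of step 5 the pooled comparison has the smaller total error. This stands against replacing the pooled column, but not against adding columns beside it.
- **The plan already helps.** Days 1–4 of the daily tabulation have matched exposure, the listings carry cohort, and SAP section 6 allows the shells to change. That makes the fix easy but does not supply it.
- **Day 8 is not a clean contrast.** A reader might infer that half the Day 8 sham denominator cannot show a device reaction. The documents do not support that. Seven days of dosing normally end on Day 7, and Visit 5 falls on Study Days 7–9, so Cohort 2 has usually stopped as well. The row also includes early terminations, who may still be treating. The Phase I statement describes the typical case only. Protocol 9.2.2 foresees unresolved reactions, and one solicited item covers any other lesion or pain of the oral mucosa, whether or not the device is in use.

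**Conclusion.** The point holds as a cheap improvement to presentation. The final shells for Tables 14.3.1.1–14.3.1.4, 14.3.2 and 14.3.3 mix two sham exposures in roughly equal parts, and no planned summary table separates them. The stated direction requires that events be more frequent, or more readily attributed, during use than after it.

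Under that condition and equal active and sham risk, the cumulative distortion is about 4, 6 or 9 points at assumed daily risks of 3%, 5% or 10%. It is clearest in the cumulative TEAE tables and in the Day 5–7 daily tabulations. It is absent on Days 1–3 and in the interim tables, and smaller and uncertain at Day 8/ET. Nothing here shows that the trial's safety conclusion would change. The argument does not extend to methemoglobin, so Table 14.3.5 is outside it.

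**What to change.** In Tables 14.3.1.1–14.3.1.4, 14.3.2 and 14.3.3, and in the daily tabulations of SAP 5.6.1, add columns for 4 Days Sham and 7 Days Sham, each next to the RD-X19 arm of the same duration. Keep the pooled Sham column and footnote it as mixed 4-day and 7-day exposure. With the same event risk in active and sham, the expected difference between each arm and its own cohort's sham is then zero at every visit and cumulatively.

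The cost is two further columns in shells that may still be modified, using a cohort variable already on the listings. The price in precision is the wider bound in step 5 for about 10 subjects per column (up to 12 with the overage), which is the reason to retain the pooled column.
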